Traditional infectious disease models of HCV disease are often based on assumptions about mixing, i.e. that individuals who are infectious and susceptible have contact with all other members of the population. Such models that are not informed by empirically based contact patterns and fail to capture the heterogeneity in individual interactions.^[35] In our study, the ability to collect data on using both blood sampling and social network will allow us to estimate incidence rates in conjunction with estimating the network itself. Our goal is to explore the network role in HCV transmission, including an examination of independent risk factors for transmission. For example how to network size, connectivity or geographic spread impact risk? What are the potential protective network effects? For example, in the rural Appalachian setting, injection drug use network studies revealed that injection of prescription opioids, cocaine, needle sharing, and degree centrality (i.e. connected network position) were associated with increased HCV risk.^[36] Public health and policy intervention that could impact HCV transmission in this case could include prevention of transition to injection among prescription opioid, as well as increased access to opioid maintenance treatment, and syringe exchange. Network position can be useful when employing network-based interventions via dissemination of information, clean needles, and naloxone.

In ETHIC, injection, sexual and social support network data will be collected from participants. Participants will also undergo HIV, HCV and STI screening. Data collected will not be used to attempt to contact network partners (see section “Protection of Third Party Data below). Respondent driven sampling (RDS), a voucher based snowballing type of recruitment will be used. An augmented social network will be generated using matching protocols between participant self-reported networks and RDS connections. Having better connection information than would be obtained through RDS in isolation allows for more variety of network indices to be examined for relevance in interventions. The accuracy of network structure is critical to appropriately inform the universe of available prevention and treatment interventions.

2) Specific aims: The goals of ‘Ending transmission of HIV, HCV, and STDs and overdose in rural communities of people who inject drugs’ (ETHIC) are to:

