- b. **PWUD surveys :** Respondent-Driven Sampling (RDS) will be utilized with the harm reduction organization client population. RDS has been widely applied to study hard to reach populations.[13-17] RDS is an efficient method that uses respondents' network connection to generate a sample that approximates a probability sample allowing for valid statistical analysis. RDS uses a small number of initial seeds (generally highly socially connected clients referred by the harm reduction organization), each of who will receive no more than six vouchers to recruit other people who have injected drugs or used opioids or stimulants to get high within the past 30 days. These seeds will be recruited by the harm reduction partners through their existing client base. All efforts will be made to ensure that seeds are diverse from a standpoint of race/ethnicity, gender, and county of residence. New seeds can be added if chains of referral stop. Respondents receive an incentive payment for their participation and an incentive for each voucher that they distribute that produces an additional eligible respondent. The process is then repeated with each new respondent. This system of incentive payments, which is crucial to RDS, also serves to maintain ongoing contact

with respondents and will aid in our retention of respondents. Potential clients who are referred by the harm reduction partners will meet with study staff who will provide eligibility screening, perform the electronic consent process, complete locator form which will be used if a future amendment for this study includes a follow up surveys and/or interviews, and confirmatory test results (SOC), and administer the survey. If consented to by the study participant, results from routine HIV/HCV screening performed for these clients by the harm reduction organization staff will be communicated to the co-PI ([name]).

- i. In addition to RDS, we will place our study recruitment flyers at spaces available to the public. These spaces will include local health departments, social services organizations, public parks, public transportation, and food pantries. The appropriate permissions will be sought from the venue operators prior to posting the flyers.

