egocentric networks (both nonsexual social and sexual) and RDS connections. Network structure will be estimated by evaluating main component size, the nodes located in the largest connected component of the network, and average component size. Measures will include the average geodesic distance between participants, network centralization (degree the network centralizes around one or a small group of participants), ranked kplex measure of cohesion, and transitivity (degree which triadic closure occurs)[21-26] Individual and network factors associated with infectious diseases will be determined.

- o) PWUD Population Size Estimation: Multiple estimators for RDS weighting for network factors will be tested for best performance, including the Volz-Heckathorn and the Successive Sampling Estimators.^[27, 28] For the Successive Sampling Estimator, we will use mixed-methods triangulation to estimate PWUD population size in the delta regional authority, including survey data, fatalities related to overdose, and drug arrest data.^[29]
- p) HCV sequencing analysis: analyses of minimum distances, maximum distances, nucleotide diversity, frequency of major haplotypes and calculations for sequence relatedness will be performed on the HVR1 quasispecies using statistical and bioinformatics toolboxes implemented in MATLAB software package version 2011B (The MathWorks, Inc., Natick, MA). The minimum distance between intra-host HCV variants will be calculated, and a minimal hamming distance for the relatedness threshold (3.7%) will be used to identify epidemiologically confirmed outbreaks, as has been previously described.^[30] Previous work by key investigators have used this approach in collaboration with the CDC to study HCV outbreaks.^[31, 32] Further analytic approaches will be considered in close collaboration with the GHOST laboratory.
- q) **Evaluation of Harm Reduction Services Referrals. Evaluation will be performed using the RE-AIM framework (Reach, Evaluation, Adoption, Implementation and Maintenance) using survey, interview and CAP program data.**
 - 1.) Reach Analysis: Descriptive analyses will be conducted initially to examine variable distributions and identify outliers, and data will be summarized using frequencies and measures of central tendency. The absolute number and proportion of participants accepting referral to the harm reduction intervention will be calculated at each assessment point (Reach: absolute (%) outcome).

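### Component sizes in the augmented network include RDS coupon ties, which put a floor under them and can inflate them strongly when self-reported ties are sparse; report them with and without coupon-only ties

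*Protocol*

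**What the plan says.** The Protocol section on social network aims states the construction: "An augmented social network will be generated using matching protocols between participant self-reported networks and RDS connections". Its reason is that "Having better connection information than would be obtained through RDS in isolation allows for more variety of network indices to be examined". Section 8, item n) repeats it, naming the tie sources as "egocentric networks (both nonsexual social and sexual) and RDS connections". On that graph, "Network structure will be estimated by evaluating main component size, the nodes located in the largest connected component of the network", plus average component size. The same item continues: "Measures will include the average geodesic distance between participants, network centralization", then a k-plex measure of cohesion and transitivity.

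On recruitment, section 4 b), item b (PWUD surveys) says that "RDS uses a small number of initial seeds", without a number. Each person receives at most six vouchers, the process repeats with each new respondent, and "New seeds can be added if chains of referral stop". Flyers, public events and online advertisements bring in further participants outside the voucher chains.

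The aims section sets the stake: "The accuracy of network structure is critical to appropriately inform the universe of available prevention and treatment interventions". Neither document plans a version of the network without coupon ties, a rule that a coupon tie must be confirmed by naming, or a comparison with the recruitment chains alone. The SAP contains no network analysis.

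**The concern.** A component is a set of people linked by some path of ties. A coupon tie exists for every voucher recruit because that is how the person entered the sample, so the recruitment forest alone already joins participants into a limited number of components. Self-reported ties can only merge these further. Part of main and average component size is therefore fixed by field decisions: how many seeds were started, how many were added when chains stopped, and how many people came in by flyer, event or advertisement.

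If participants rarely name each other, a large main component could reflect the circulation of vouchers more than the density of ties that participants report. A reader choosing network-based interventions could then take the population to be more cohesive than the survey answers show.

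**Working it through.** The documents state no network figure, so there is none to reproduce. The check has two parts: an exact bound, and a simulation of how far above that bound the measures can move.

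**Inputs.** From the Protocol: at most 6 vouchers per person and 100 to 800 survey participants (section 4), and 173 participants enrolled between 8/2017 and 7/2019 (section 9). Assumed, because the documents are silent: 5 to 40 seeds, 0-50% of non-seed participants recruited without a voucher, 20-25% of vouchers redeemed, and mean self-reported degree d between participants of 0 to 4, with these ties placed at random.

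**1. Exact bound.** Let R = seeds (including any added later) + non-voucher recruits. Everyone else is tied to a recruiter, so:

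- number of components ≤ R
- average component size ≥ n / R
- main component ≥ n / R, rounded up

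Named people who are not participants do not break the bound, because each is tied to a participant.

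For n=173 with all non-seeds on vouchers:

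- 5 seeds: 173/5 = 34.6
- 10 seeds: 173/10 = 17.3
- 20 seeds: 173/20 = 8.65
- 40 seeds: 173/40 = 4.3

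For n=173 with 10 seeds and some non-voucher recruits:

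| Non-voucher share | R | Minimum average size |
|---|---|---|
| 0% | 10 | 17.3 |
| 10% | 26 | 6.65 |
| 25% | 51 | 3.39 |
| 50% | 92 | 1.88 |

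The floor always exists, but non-voucher recruitment lowers it quickly.

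**2. Main component with and without coupon ties** (n=173, 25% redemption, no non-voucher recruits):

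| Mean reported degree | Reported ties only | Planned graph, 5 seeds | Planned graph, 20 seeds |
|---|---|---|---|
| 0.5 | 4% | 99% | 96% |
| 1 | 17% | 100% | 99% |
| 2 | 78-79% | 100% | 100% |
| 4 | 98% | 100% | 100% |

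The reported network goes from fragmented to almost fully connected, while the planned measure stays at 96-100%. Results at 22% redemption are nearly the same.

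**3. Average component size.** At d=0.5 in the same setting it is 1.3 on reported ties, against about 120 (5 seeds) or 46 (20 seeds) on the planned graph. At n=100 and d=2 it is about 6 against 99 (5 seeds) or 74 (20 seeds). This measure stays sensitive to the number of seeds after the main component has stopped being so.

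**4. Effect of non-voucher recruitment** (n=100; main component on the planned graph):

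| d | Seeds | 0% | 25% | 50% | Reported ties only |
|---|---|---|---|---|---|
| 0.5 | 5 | 99% | 80% | 45% | 6-7% |
| 0.5 | 20 | 88% | 60% | 33% | 6% |
| 1 | 5 | 100% | 92% | 78% | 19-20% |
| 1 | 20 | 97% | 87% | 73% | 19-21% |
| 4 | 5 or 20 | 100% | 100% | 99% | 98% |

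Inflation falls as non-voucher recruitment rises, but at low d it is still large with half of the non-seed participants recruited that way.

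**The case against.** The strongest reply is that a coupon tie is itself evidence of contact. RDS works through existing acquaintances, and nothing in the documents suggests that vouchers pass between strangers. Long chains from few seeds need real paths. This stands. It means that the graph without coupon-only ties is not simply the true network, and a demand to read structure from self-report alone would go too far.

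A reader might also infer that the component measures are largely set by seed numbers. With no reported ties at all they are: at n=173 and 20-25% redemption the main component falls from 52-67% with 5 seeds to 15-19% with 20, about 3.5-fold. The plan does add reported ties, however, and even at d=0.5 the gap shrinks to 99% versus 96%. For main component size, the presence of coupon ties then matters far more than the number of seeds.

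Nor do the calculations support a claim that coupon ties generally shorten distances. At d=0.5 they lengthen the mean geodesic distance among connected pairs (6.4-7.2 against 1.7-1.9) because they connect more people; they shorten it only at d of 2 or more. Coupon trees contain no triangles, so they create no triadic closure by themselves. Effects on k-plex cohesion and centralization were not calculated.

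Two further points carry some weight. The network aim is exploratory, and the documents plan no comparison of component sizes over time or between sites. The matching rule is also deferred to cited methods that are not reproduced, so it is not certain that every unmatched coupon tie is kept. The wording reads that way, since RDS connections are named as a tie source and no exclusion is given.

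**Conclusion.** The point holds in a bounded form. Coupon ties are part of the planned graph, and they fix a ceiling on the number of components and a floor under both component-size measures. That part needs no assumption beyond reading the text as keeping all coupon ties. The inflation can be strong when matched self-reported ties are sparse: main component about 96-100% against 4-17% at mean degree 0.5 to 1, with n=173, 5 to 20 seeds and no non-voucher recruits. It nearly disappears for main component size at degree 4 and weakens as non-voucher recruitment rises. Average component size is affected over a wider range.

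Seed number, non-voucher share and tie density are not in the documents, and the simulated reported ties are random and independent of coupon ties. The figures therefore show what can happen and do not forecast this study's result. They do not show that the measures are mainly a product of seed numbers, or that the augmented graph carries no information on cohesion. This is an inexpensive improvement to an exploratory analysis; it does not invalidate the network aim.

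**What to change.** In section 8, item n):

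- Store the source of each tie (coupon only, named only, or both) before the name file and cross-walk are destroyed as described in section 12 a), Protection of Third Party Data. After that step the distinction may not be recoverable.
- Report main and average component size, and the other listed measures computed on the same graph, both with and without coupon-only ties.
- Report the recruitment forest alone as a benchmark, with the numbers of seeds (initial and added) and of non-voucher recruits.
- Draw conclusions about cohesion only where the two graphs agree; otherwise present the two results as a range.

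The cost is one extra variable and further runs of the same code on data already to be collected. There are two limits. The graph without coupon-only ties drops some real contacts that nobody named. It may also still contain many coupon ties, because recruiters may name their recruits: if 90% of coupon ties were also named (an assumption), its main component at n=173, 22% redemption and d=0.5 would still be 93% with 5 seeds or 89% with 20. The benchmark and the counts by source let a reader see when that is so.

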The prevention opioid overdose and transmission of infectious diseases related to injection drug use will depend upon increased access to opioid use disorder treatment such as medication assisted therapy (MAT), hepatitis C treatment as well as testing, screening and linkage to these services. As of the submission of this protocol there are only 26 DATA 2000 waivered buprenorphine prescribers in the study region and no methadone clinics. Eight of the 16 counties are designated “MAT Deserts”, i.e. no MAT provider available per the Illinois Department of Human Services. This lack of access was reflected in survey data where only 13% of respondents had received any substance use disorder support in the past 30 days and 70% were unsure or felt that it would be difficult to access buprenorphine for treatment if they wanted it. In regards to Hepatitis C, the prevalence of HCV+ Ab in our study was high (47.8%) and access to treatment was low (10.4%). As of the submission of this protocol there were only 3 infectious diseases specialists and 4 gastroenterologists with active licenses in the study region according to the Illinois Department of Professional Regulation.

Survey respondents reported low access / utilization of general medical care (24% had not received care in the past 6 months) citing barriers including transportation (40.9%), and fear of being disrespected (41.6%) in the healthcare environment. The largest percentage of those receiving healthcare (35%) reported obtaining it in emergency departments (EDs). Our qualitative data revealed many problematic encounters in that setting, citing breaches of trust by ED providers, such as disclosures of protected health information to law enforcement and child protective services, as well as stigmatizing and humiliating provider-patient interactions. These experiences and perspectives were substantiated by commentary from healthcare providers whom we interviewed.

To promote HCV, MAT, and PWUD health trained ED workforce development we will utilize the Extension for Community Healthcare Outcomes (ECHO) model. ECHO was developed in 2003 at the University of New Mexico (UNM) by [name], a hepatologist, as a way to provide hepatitis C patients with timely care. Using videoconferencing technology, the ECHO

model brings community-based PCPs together with subspecialist teams from academic medical centers for “telementoring” and collaborative, curriculum-driven, case-based training. Unlike a webinar, participants and facilitators alike can see, hear, and learn from each other, fostering a more engaging and interactive learning experience. Modeled after medical “rounds,” PCPs present challenging patient cases, sharing how they have implemented suggested practices and identifying issues with which they continue to struggle. Many of these discussions focus on issues such as how to approach difficult conversations with patients, how to work with patients to scale goals to be more practical and achievable, and building trust.

Since 2008, the Project ECHO model has been leveraged to train thousands of clinicians in many different specialty areas around the country. To date there are a total of 287 partners in more than 35 countries replicating the ECHO model on 70 different categories. The highly successful ECHO model can be leveraged and applied to train clinicians in a manner that is very scalable, in order to meet the ever increasing medical care needs.

The literature to date supports the effectiveness of the ECHO model in improving PCP outcomes, including growing knowledge, enhancing self-efficacy, improving job satisfaction, and increasing empowerment to treat complex, chronic conditions including hepatitis C and opioid use disorder.¹⁻¹⁰ While the literature on the broader impact of ECHO continues to grow, early studies point to the model being able to successfully improve chronic disease management, boost disease management in primary care to be on par with subspecialists, and achieve cost savings. ^{6,11-14}

Mapping of current primary care, psychiatry, and emergency medicine sites in the Delta region was performed to identify potential ECHO sites. Data sources included a survey performed by the Southern Illinois School of Medicine (SIUSOM) Office of Continuing Professional Development (CPE) of primary care providers, active license listings from the Illinois Department of Financial and Professional Regulation and the Illinois Department of Human Services. At the time of this protocol development there were 181 general practitioners (family medicine, internal medicine, etc.) and 16 psychiatrists with active licenses in the study area.

There were a total of 96 clinical sites, including 26 family medicine practices, 23 rural health clinics and 24 FQHCs

Aim:

Build capacity for HCV management, substance use screening, referral, and medication-assisted treatment through the Extension of Community Healthcare Outcomes (ECHO) model targeted at PWUD-preferred service settings.

Sub aim:

We will develop and implement an innovative ECHO curriculum targeted to emergency medicine providers on PWUD healthcare (ECHO-ED)

Sites conducting research:

University of Chicago

Southern Illinois University (SIUSOM)

Methods:

ECHO-ED curriculum development:

We will adapt existing CME materials to develop an ECHO-ED curriculum covering the following topical areas: prescription monitoring, opioid prescribing recommendations, non-opioid pain control in the ED and after leaving the ED, an introduction to MAT and warm handoff to resources, take home naloxone, skin and soft tissue infection, screening for infectious diseases, communicating with patients that have OUD and legal implications. Additional topical areas identified in the Pre-ECHO Key informant interviews will also be addressed. Key informant interviews will also serve to identify potential barriers to providing the ECHO intervention, including appropriateness of the ECHO format such as scheduling around ED shifts that can inform the delivery of the intervention. The curriculum will be reviewed by representatives from the Illinois Poison Center and the Illinois College of Emergency Physicians for accuracy and appropriateness.

ECHO Implementation :

ECHO-Chicago will implement an evidence-based ECHO-HCV curriculum and the ECHO-ED series twice annually. Evidence based ECHO-MAT curriculum will be provided by the Southern Illinois University Department of Psychiatry twice annually. Participant will join hour-long weekly sessions via the Zoom video-conferencing platform. Sessions will be facilitated by a multidisciplinary expert team.

Study Activities

Interviews/Focus Groups:

All interviews will be conducted either face to face in a private office/space, over the telephone or Zoom. Focus groups will be conducted over Zoom. All interviews and focus groups will be audibly recorded without the collection of any identifiers and then transcribed. The audio recordings will be stored for 5 years and then destroyed. We will not collect any PHI during the interviews described below. Following the interviews, all subjects will be asked to complete a brief demographic survey. The information captured through this survey will be used to help us contextualize the background and general traits of these participants.

Pre ECHO-ED

Up to 10 clinical providers will be asked to take part in an interview prior to the ECHO-ED development. These providers will include emergency medicine physicians, nurses, pharmacists, and primary care providers who will serve as key informants to the development of the ECHO-ED curriculum. The interview will take approximately 30 minutes to complete.

Recruitment: A study flyer with contact information will be distributed to clinical sites in southern Illinois by ETHIC Operations Partners Committee, namely Southern Illinois Healthcare and the Center for Rural Health and Social Services Development, as well as the Illinois Hospital Association and the Illinois College of Emergency Physicians.

Post-ECHO Trainee

Up to 15 providers who have participated in the ECHO curriculum (4-5 for each curriculum) will be interviewed as a component of implementation evaluation for the ECHO intervention (i.e. ECHO as a delivery mechanism for clinical training). The interview will be help to elicit barriers

and facilitators from the trainee perspective. The interview will take approximately 60 minutes to complete.

Recruitment: A slide with study information will be posted by the ECHO administration group during each of the curriculum presentations to seek interested providers. The slide will contain study contact information.

Post-ECHO Expert Trainer

Up to 9 ECHO expert trainers (ie gastroenterologist, addiction specialist, emergency medicine physician) at the ECHO hubs (University of Chicago and SIUSOM) covering each curriculum will be invited to participate in a focus group as a component of implementation evaluation for the ECHO intervention (i.e. ECHO as a delivery mechanism for clinical training). The focus group guide will be developed to elicit barriers and facilitators from the trainer perspective. The focus group will take approximately 40 minutes to complete.

Recruitment: Participants will be recruited from the team of expert trainers leading the ECHO curriculum supported by the University of Chicago and SIUSOM ECHO programs. They will be directed contacted via email by the study PIs.

Program Sustainability Assessment Tool (PSAT)

Up to 10 clinical directors / supervisors at ECHO trainee sites will be invited to complete the PSAT, which is a 40 question self-assessment. The PSAT evaluates the sustainability capacity of ECHO based training in the setting (i.e. maintenance).¹⁶ The PSAT covers eight sustainability domains (environmental support, funding sustainability, communications, strategic planning, partnerships, strategic planning, organizational capacity and program evaluation) and takes approximately 10-15 minutes to complete. The PSAT will be administered at baseline and after completion of at least 1 ECHO curriculum at their clinical site via a RedCap survey link.

Recruitment: Clinical directors will be informed of the opportunity to participate via notification through the ECHO programs. Clinical directors will receive an email which will be sent through the ECHO programs.

Additional Data Elements

In addition to the data collected above, we will also receive anonymous responses provided in

the surveys (150 surveys total as approximately 30-50 surveys are expected per year) which are administered to all trainees before and after ECHO training. As standard of care in ECHO, these surveys measure effectiveness of the training by asking questions which will measure knowledge of the subject matter, self-efficacy, and acceptability of the intervention, intervention appropriateness, and feasibility of the intervention. As part of the study data from ECHO-Chicago we will receive anonymous survey data from the program which will include program data regarding attendance of ECHO sessions and the zip code of the place of practice. No individual identifiers will be received from ECHO-Chicago

Subjects:

Inclusion criteria:

Males and females age \geq 18 years old, English speaking, employed in the study region (southern 16 counties: Alexander, Franklin, Gallatin, Hamilton, Hardin, Jackson, Johnson, Massac, Perry, Pope, Pulaski, Randolph, Saline, Union, White, and Williamson) as well one of the clinical provider types listed above (family medicine, primary care, internal medicine, psychiatry, emergency medicine, social work, case manager, physician, mid-level).

Exclusion criteria:

Males and females $<$ 18 years old, non-English speaking, unable to provide informed consent and not employed as described above.

Incentives

Interviewees and PSAT survey completers will be offered a \$40 gift card for their participation.

Informed consent:

Oral consent will be obtained from those who take part in the study interviews.

Electronic consent will be obtained from those who complete the PSAT.

A waiver of consent will be requested for the anonymous survey data

Potential risks and benefits to subjects:

A minimal risk of loss of confidentiality exists for this study. PHI will not be linked to any of the responses given in surveys/interviews. Limited PHI will be collected to allow for communication during interviews, surveys and to allow for payment. PHI will be destroyed after the study is complete.

Data Analysis:

- a. Reach: Reach will be defined by the absolute number of ECHO trainees participating in the first session of each ECHO curriculum. The proportion of providers reached will be calculated using the number of ECHO trainees participating divided by the number of eligible providers for the respective topic areas as estimated in section 1.g) above.
- b. Effectiveness Analysis: Effectiveness of each ECHO curriculum type will be based upon change in knowledge, self-efficacy, stigma, and adoption of practice change based on aggregate data received from the program from the Pre-and Post-ECHO Provider Survey. Paired t-tests with an alpha of .05 will be conducted to assess absolute change in knowledge, self-efficacy, stigma, and practice change.
- c1. Adoption of Practice Change: The degree of acceptability, appropriateness, and feasibility of adopting practice change for MAT, HCV and ED as promoted by the ECHO curriculum will be calculated from the trainees surveys.
- c2. Adoption of the ECHO Intervention: In contrast to adoption of training into clinical practice as discussed in the evaluation of effectiveness of the ECHO intervention, the adoption of the ECHO intervention as a mechanism for workforce capacity development will be measured by the proportion of ECHO trainees that attend 75% of live sessions, or in the case of ECHO-ED 75% of all session including recorded sessions.
- d. Implementation: The assessment of implementation fidelity for each ECHO delivery for each topical area will be performed using qualitative measures collected in the Post-ECHO Trainee interviews and Post-ECHO Expert Trainer focus group, as well as through direct session

observation using a predetermined ECHO checklist. Interviews will be transcribed and will be analyzed using a deductive thematic approach using NVivo. Each transcript will be coded by one coder; for additional fidelity, a second coder will code a subset of transcripts. Discrepancies will be resolved through discussion.

e Maintenance: The extent to which the ECHO intervention is valued and promoted subsequent to the study by clinical care leadership will be assessed by the PSAT tool as administered to clinical supervisors at participating ECHO sites. The PSAT is a Likert-scale based 40 item survey that is scored based on average rating across eight domains.

References:

